Grade 2 Requires infusion interruption but responds promptly to symptomatic treatment (e.g., antihistamines, NSAIDS, narcotics, IV fluids); prophylactic medications indicated for <=24 hrs	
Stop Infusion and monitor symptoms. Additional appropriate medical therapy may include but is not limited to:
 
 IV fluids Antihistamines NSAIDS Acetaminophen Narcotics 
Increase monitoring of vital signs as medically indicated until the subject is deemed medically stable in the opinion of the investigator. If symptoms resolve within one hour of stopping drug infusion, the infusion may be restarted at 50% of the original infusion rate (e.g., from 100 mL/hr to 50 mL/hr). Otherwise dosing will be held until symptoms resolve and the subject should be premedicated for the next scheduled dose.
 
Subjects who develop Grade 2 toxicity despite adequate premedication should be permanently discontinued from further trial treatment administration.
	
Subject may be premedicated 1.5h (\pm 30 minutes) prior to infusion of pembrolizumab (MK-3475) with:
 
Diphenhydramine 50 mg po (or equivalent dose of antihistamine).
 
Acetaminophen 500-1000 mg po (or equivalent dose of antipyretic).

Grades 3 or 4 Grade 3: Prolonged (i.e., not rapidly responsive to symptomatic medication and/or brief interruption of infusion); recurrence of symptoms following initial improvement; hospitalization indicated for other clinical sequelae (e.g., renal impairment, pulmonary infiltrates) Grade 4: Life-threatening; pressor or ventilatory support indicated	
Stop Infusion. Additional appropriate medical therapy may include but is not limited to:
 
 IV fluids Antihistamines NSAIDS Acetaminophen Narcotics Oxygen Pressors Corticosteroids Epinephrine 
Increase monitoring of vital signs as medically indicated until the subject is deemed medically stable in the opinion of the investigator. Hospitalization may be indicated.
 
Subject is permanently discontinued from further trial treatment administration.
	No subsequent dosing
Appropriate resuscitation equipment should be available in the room and a physician readily available during the period of drug administration.		

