9.0 TRIAL FLOW CHART

9.1 Study Flow Chart

Trial Period:	Screening Phase	Treatment Cycles ^a						End of Treatment	Post-Treatment		
		1	2	3	4	To be repeated beyond 6 cycles		Discon	Safety Follow-up	Follow Up Visits ^b	Survival Follow Up ^c
						5	6				
Scheduling Window (Days) ^d :	-28 to -1		± 3	± 3	± 3	± 3	± 3	± 3	± 7	± 7	± 7
Administrative Procedures											
Informed Consent ^e	X										
Inclusion/Exclusion Criteria	X										
Demographics and Medical History	X										
Prior and Concomitant Medication Review ^f	X	X	X	X	X	X	X	X	X		
Clinical Procedures/Assessments											
Review Adverse Events ^g	X	X	X	X	X	X	X	X	X	X	
12-Lead ECG	X										
Physical Examination	X	X	X	X	X	X	X	X			
Height, Weight, and Vital Signs (T, P, RR, BP) ^h	X	X	X	X	X	X	X	X			
ECOG Performance Status	X	X	X	X	X	X	X	X			
Post-study Anticancer Therapy Status									X	X	
Survival Status											X
Trial Treatment Administration											
Pembrolizumab ⁱ		X	X	X	X	X	X				
Laboratory Procedures/Assessments:											
Pregnancy Test – Urine or Serum β-HCG ^j	X										
PT/INR and aPTT ^k	X										
CBC with Differential ^l	X		X	X	X	X	X ^l	X	X ^l		

Trial Period:	Screening Phase	Treatment Cycles ^a						End of Treatment	Post-Treatment		
		1	2	3	4	To be repeated beyond 6 cycles			Safety Follow-up	Follow Up Visits ^b	Survival Follow Up ^c
Treatment Cycle/Title:	Screening (Visit 1)					5	6				
								At time of discon	30 days post discon	Every 6 weeks post discon	Every 12 weeks
Scheduling Window (Days) ^d :	-28 to -1	± 3	± 3	± 3	± 3	± 3	± 3	± 3	± 7	± 7	± 7
Chemistry Panel ¹	X		X	X	X	X	X ¹	X	X ¹		
Urinalysis ¹	X										
T3, FT4 and TSH ¹	X		X		X		X		X		
Serum carcinoembryonic antigen (CEA) ¹	X		X		X		X ¹				
Serum CA 19-9 ¹	X		X		X		X ¹				
Blood for Genetics ^m		X									
Correlative Blood Samples (DNA) ⁿ		X	X	X				X			
Correlative Blood Samples (RNA) ⁿ		X	X	X				X			
Correlative Blood Samples (plasma) ⁿ		X									
Correlative Blood Samples (serum) ⁿ		X									
Efficacy Measurements											
Tumor Imaging ^o	X		X		X		X	X ^p		X	
Tumor Tissue Collection											
Archival and/or Newly-Obtained Tissue Collection	X	-----X----- ^q						X			

- a. Unless otherwise specified, assessments/procedures are to be performed on Day 1 and prior to the first dose of treatment for each cycle.

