- b. In subjects who discontinued study therapy without documented disease progression, every effort should be made to continue monitoring their disease status by radiologic imaging every 6 weeks (\pm 7 days) if prior to 1 year or every 9 weeks (\pm 7 days) if after 1 year, until (1) the start of new anti-cancer treatment, (2) disease progression as assessed by imaging , (3) death, or (4) the end of the study, whichever occurs first.
- c. After the start of new anti-cancer treatment or documented disease progression by the imaging , the subject should be contacted by telephone every 12 weeks to assess for survival status. Note: All efforts should be made to ensure telephone contact occurs at least 90 days post discontinue to capture SAEs
- d. Unless otherwise specified, the window for each visit is \pm 3 days. Cycle 1 treatment must be given within 3 days of enrollment.
- e. Written consent must be obtained prior to performing any protocol specified procedure. Results of a test performed prior to the subject signing consent as part of routine clinical management are acceptable in lieu of a screening test if performed within the specified time frame (e.g., within 28 days prior to the first dose of trial treatment).
- f. Prior medications – Record all medications taken within 28 days of screening visit. Concomitant medications – Enter new medications started during the trial through the Safety Follow-up visit. Record all medications taken for SAEs
- g. Record all AEs occurring within 30 days after the last dose of trial treatment. Report all SAEs (related and unrelated to trial treatment) and ECIs occurring up until 90 days after the last dose of trial treatment or the start of new anti-cancer treatment, whichever comes first. Afterwards, report only SAEs and ECIs that are related to trial treatment.
- h. Height will be measured at Visit 1 only. Vitals Signs include temperature, pulse, respiratory rate, and blood pressure.
- i. Pembrolizumab should be administered on Day 1 of each three week cycle after all procedures/assessments have been completed.
- j. For women of reproductive potential, a serum pregnancy test should be performed within 72 hours prior to first dose of trial treatment. A urine test can be considered if serum is not appropriate. Pregnancy tests (serum and/or urine tests) should be repeated if required by local guidelines.
- k. Coagulation factors (PT/INR and aPTT) should be tested as part of the screening procedures for all subjects.

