- l. Laboratory tests for screening are to be performed within 10 days prior to the first dose of trial treatment.
After Cycle1, lab samples can be collected up to 72 hours prior to the scheduled time point. To be repeated every 2 cycles after Cycle 6. Unresolved abnormal labs that are drug relatedAEs should be followed until resolution. Labs do not need to be repeated after the end of treatment if labs are within normal range. Serum CEA and CA 19-9 should be collected at screening (baseline) and every 6 weeks (conducted at corresponding study visits) through Week 24 (6 months). After Week 24, serum CEA and CA19-9 should be collected every 12 weeks until study treatment discontinuation..
- m. This sample should be drawn for planned genetic analysis of DNA and drug response unless there is either a documented law or regulation prohibiting collection, or unless the IRB/IEC does not approve of the collection of the sample for these purposes.
- n. Whole blood sample for correlative studies should be collected at Cycle 1, Day 1- Pre-dose, Cycle 2 Day 1- Pre-dose, Cycle 3 Day 1 Pre-dose and again at treatment discontinuation. Blood for serum and blood for plasma to be collected only prior to Cycle 1 Day 1.
- o. Baseline tumor imaging will be performed within 14 days prior to enrollment. Scans performed as part of routine clinical management are acceptable for use as the baseline scan if they are of diagnostic quality . The exact same image acquisition and processing parameters should be used throughout the study. The first on-study imaging time point will be performed 6 weeks (\pm 7 days) or earlier if clinically indicated and will continue to be performed every 6 weeks (\pm 7 days) regardless of any treatment delays. Following week 24 (6 months), imaging time point will occur every 12 weeks (\pm 7 days) while the subject remain on trial. Imaging timing should follow calendar days. On-study scans should be submitted immediately to the imaging .
- p. In subjects who discontinue study therapy without verified disease progression, a radiologic evaluation should be performed at the time of treatment discontinuation (i.e., date of discontinuation \pm 4 week window). If a previous scan was obtained within 4 weeks prior to the date of discontinuation, then a scan at treatment discontinuation is not required.

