10.2 Assessing and Recording Adverse Events

An adverse event is defined as any untoward medical occurrence in a patient or clinical investigation subject administered a pharmaceutical product and which does not necessarily have to have a causal relationship with this treatment. An adverse event can therefore be any unfavorable and unintended sign (including an abnormal laboratory finding, for example), symptom, or disease temporally associated with the use of a medicinal product or protocol-

specified procedure, whether or not considered related to the medicinal product or protocol-specified procedure. Any worsening (i.e., any clinically significant adverse change in frequency and/or intensity) of a preexisting condition that is temporally associated with the use of the Merck's product, is also an adverse event.

Changes resulting from normal growth and development that do not vary significantly in frequency or severity from expected levels are not to be considered adverse events. Examples of this may include, but are not limited to, teething, typical crying in infants and children and onset of menses or menopause occurring at a physiologically appropriate time.

Merck product includes any pharmaceutical product, biological product, device, diagnostic agent or protocol-specified procedure, whether investigational (including placebo or active comparator medication) or marketed, manufactured by, licensed by, provided by or distributed by Merck for human use.

Adverse events may occur during the course of the use of Merck product in clinical trials or within the follow-up period specified by the protocol, or prescribed in clinical practice, from overdose (whether accidental or intentional), from abuse and from withdrawal.

Adverse events may also occur in screened subjects during any pre-allocation baseline period as a result of a protocol-specified intervention, including washout or discontinuation of usual therapy, diet, placebo treatment or a procedure.

Progression of the cancer under study is not considered an adverse event unless it is considered to be drug related by the investigator.

All adverse events will be recorded from the time the consent form is signed through 30 days following cessation of treatment and at each examination on the Adverse Event case report forms/worksheets. The reporting timeframe for adverse events meeting any serious criteria is described in section 7.2.3.1.

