10.2.3.2 Events of Clinical Interest

Selected non-serious and serious adverse events are also known as Events of Clinical Interest (ECI) and must be recorded as such on the Adverse Event case report forms/worksheets and reported within 24 hours to IRB and within 2 working days to Merck Global Safety. (Attn: Worldwide Product Safety; [contact])Events of clinical interest for this trial include:

1. an overdose of Merck product, as defined in Section 10.2.1 - Definition of an Overdose for This Protocol and Reporting of Overdose to Merck, that is not associated with clinical symptoms or abnormal laboratory results.
2. an elevated AST or ALT lab value that is greater than or equal to 3X the upper limit of normal and an elevated total bilirubin lab value that is greater than or equal to 2X the upper limit of normal and, at the same time, an alkaline phosphatase lab value that is less than 2X the upper limit of normal, as determined by way of protocol-specified laboratory testing or unscheduled laboratory testing.*

***Note:** These criteria are based upon available regulatory guidance documents. The purpose of the criteria is to specify a threshold of abnormal hepatic tests that may require an additional evaluation for an underlying etiology.

1. Additional adverse events:

ECIs (both non-serious and serious adverse events) identified in this guidance document from the date of first dose through 90 days following cessation of treatment, or 30 days after the initiation of a new anticancer therapy, whichever is earlier, need to be reported within 24 hours to IRB and within 2 working days to Merck Global Safety. (Attn: Worldwide Product Safety; [contact]), regardless of attribution to study treatment, consistent with standard SAE reporting guidelines.

Subjects should be assessed for possible ECIs prior to each dose. Lab results should be evaluated and subjects should be asked for signs and symptoms suggestive of an immune-related event. Subjects who develop an ECI thought to be immune-related should have additional testing to rule out other etiologic causes. If lab results or symptoms indicate a possible immune-related ECI, then additional testing should be performed to rule out other etiologic causes. If no other cause is found, then it is assumed to be immune-related.

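### Note l lets the Safety Follow-up CBC and chemistry be skipped after normal labs, leaving a usually short part of the 30-day AE window with no required draw

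*Combined protocol and SAP*

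**What the plan says.** In the Section 9.1 grid, the rows for "CBC with Differential" and for the chemistry panel have a plain X at discontinuation and an X with a cell-level marker for note l at Safety Follow-up. Neither panel is marked at the later Follow Up Visits or in Survival Follow Up.

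Note l contains the waiver: "Labs do not need to be repeated after the end of treatment if labs are within normal range". It does not say which draw or which analytes must be normal. The sentence just before it keeps known problems in view: "Unresolved abnormal labs that are drug relatedAEs should be followed until resolution".

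The safety definitions extend past the last dose:

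- Flow chart note g: "Record all AEs occurring within 30 days after the last dose of trial treatment".
- Section 10.2 includes in its AE definition "any unfavorable and unintended sign (including an abnormal laboratory finding, for example".
- Section 10.2.3.2 defines the hepatic ECI by laboratory values alone: "an elevated AST or ALT lab value that is greater than or equal to 3X the upper limit of normal", together with bilirubin at least 2 times and alkaline phosphatase below 2 times the upper limit.

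The timing of the Safety Follow-up visit is given in two ways. Section 10.1.5.4.1 counts about 30 days from the last dose, or earlier if new anti-cancer treatment starts. The flow chart column header counts 30 days from discontinuation. Section 10.1.5.3 lets the discontinuation and safety visits merge when they fall together.

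**The concern.** A patient with normal labs at discontinuation is one in whom any later abnormality would be new. Section 8.2.1.2 warns that immune-related events can start after dosing has ended. Under note l the plan asks for no further CBC or chemistry in such a patient, although AEs are still being recorded and the hepatic ECI can be recognised only from a blood result. A symptom-free rise in AST/ALT, creatinine or glucose, or a new cytopenia, would then enter the data only if someone chose to test. Whether a value exists at the safety visit would depend partly on the earlier result.

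What is at stake is the completeness of late laboratory safety data. Section 11.1.2 names laboratory tests among the safety parameters, to be summarised descriptively. The ORR analysis and the sample size do not depend on these draws.

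**Working it through.** **Step 1. Does the waiver reach the Safety Follow-up draw?** In the CBC row the marker for note l stands on two cells only: Cycle 6 and Safety Follow-up. The Cycle 6 marker matches the sentence in note l that moves labs to every second cycle. The Safety Follow-up marker matches the sentences on what happens once treatment ends. The chemistry row has the same pattern (the marker prints as a numeral 1 and is read as the same letter). The discontinuation cell is unmarked, so that draw stands. Thyroid tests have a plain X at Safety Follow-up and are read here as required; they are outside this point.

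**Step 2. Does another section require the panels?**

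| Provision | Reach |
|---|---|
| Note l, unresolved drug-related labs | Abnormalities already found |
| Section 10.1.5.4.1, AEs above Grade 1 | AEs already known |
| Section 10.1.3 and Section 10.2.3.2, lab review | Tied to each dose; none after the last |
| Section 10.1, unscheduled procedures | Investigator's discretion |
| Section 9.1, later follow-up columns | No CBC or chemistry |

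None requires a CBC or chemistry in a symptom-free patient after a normal discontinuation draw.

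**Step 3. Length of the gap.** Let day 0 be the last dose and D the day of the discontinuation draw. The AE window ends on day 30 (note g), so the untested part is G = 30 − D. Inputs from Section 9.1: 21-day cycles and a ±3-day window at discontinuation. The day on which treatment stops is an assumption; the documents give no distribution.

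| Case | D | G = 30 − D | Share of 30 days |
|---|---|---|---|
| Stops at next planned dose | 21 | 9 | 30% |
| Same, visit window | 18 to 24 | 12 to 6 | 40% to 20% |
| Visits coincide (Section 10.1.5.3) | 30 | 0 | 0% |
| Stops at the infusion | 0 | 30 | 100% |

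The last case can arise after a Grade 3 or 4 infusion reaction, for which Table 4 in Section 8.4.1 says "Subject is permanently discontinued from further trial treatment administration". Note l also says "After Cycle1, lab samples can be collected up to 72 hours prior to the scheduled time point". Stacking that on a visit 3 days early gives D = 21 − 3 − 3 = 15 and G = 15, an outer combination not relied on here.

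**Step 4. What a Safety Follow-up draw on day S would cover.** AE-window days covered = max(0, min(S, 30) − D).

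- Section 10.1.5.4.1 timing, S = 30 and D = 21: 30 − 21 = 9 days, the whole ordinary gap. With S from 23 to 37 and D from 18 to 24, the range is 0 (S = 23, D = 24) to 12 (S at least 30, D = 18).
- Flow chart header timing, S = D + 30 ± 7: the draw falls 23 to 37 days after discontinuation. For D = 21 that is day 51 (44 to 58) from the last dose, beyond the AE window. It falls by day 30 only if D + 23 ≤ 30 at the earliest, that is D ≤ 7. For D up to 24 it is no later than 24 + 37 = day 61, so still within the 90-day ECI window unless new therapy has started.

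**Step 5. Scale.** After Cycle 6, note l spaces required labs two cycles apart: 2 × 21 = 42 days. After a day-21 draw, 90 − 21 = 69 days of ECI window remain, of which the draw covers 9 (9/69 = 13%).

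**The case against.** The strongest defence is that the rule is explicit and adapted to risk: patients with abnormal labs are retested, drug-related abnormalities are followed to resolution, AEs are reviewed at a mandatory visit, and the investigator can test at any time. The ordinary gap of 9 days is short against the 42 days accepted between required draws late in treatment, and even the 30-day case is shorter than that. This stands, and it is why the point is minor. It does not remove the gap, because none of these provisions tests a symptom-free patient.

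Note l might also be read as ending repeats only once the scheduled post-treatment labs are normal, in which case the Safety Follow-up draw is still due. The placement of the marker favours the waiver reading, but the sentence is loose enough for sites to differ. That is itself a reason to reword it.

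The affected group may be small. The waiver needs results within normal range, while Table 1 in Section 8.1.2 admits patients with haemoglobin down to 9 g/dL and AST/ALT up to 2.5 or 5 times the upper limit. Patients with such values may never qualify for the waiver. That stands.

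A reader might go further and infer that the plan materially under-counts late toxicity, or that most of the AE window goes untested. The documents do not support either. They give no count of affected patients and no distribution of stopping times, and the full 30-day gap needs treatment to stop at the infusion itself. Nor can the warning about events months after dosing justify much here: restoring the draw covers only 13% of the remaining ECI window in the ordinary case.

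**Conclusion.** The concern holds as a cheap improvement of minor severity. As written, note l allows the Safety Follow-up CBC and chemistry to be omitted after normal labs, and no other provision replaces them. Counted from the last dose, the gap is about 9 days in the ordinary case, 6 to 12 with the visit window, nil when the visits coincide, and about 30 days at the extreme.

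These figures assume that Section 10.1.5.4.1 governs the visit date and that the discontinuation draw is taken when treatment stops. If the flow chart header governs, the length of the gap is unchanged, but the waived draw would mostly fall after the AE window, where its value would be for ECI detection.

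The consequence is possible under-recording of late, symptom-free laboratory AEs and hepatic ECIs in a descriptive safety summary. How many patients this touches cannot be derived.

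**What to change.** Replace the waiver sentence in note l with:

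> CBC and chemistry are collected at the Safety Follow-up visit (about 30 days after the last dose, Section 10.1.5.4.1) from all treated subjects, except where the Discontinuation Visit coincides with it (Section 10.1.5.3); no further repeats are needed after that visit if those results are within normal range.

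Keep the sentence on following unresolved drug-related abnormalities. Change the Safety Follow-up column header in Section 9.1 so that its 30 days run from the last dose rather than from discontinuation. Without this second edit the grid and Section 10.1.5.4.1 would still disagree on when the sample is due.

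The cost is two small text edits and one extra routine CBC and chemistry sample for patients who would otherwise be waived, often only about 9 days after their previous draw. The visit is already mandatory and the grid already marks a thyroid blood test there, so no new visit or assay is needed. The change adds no testing between days 30 and 90, which would remain at the investigator's discretion.

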5.0 TRIAL DESIGN

5.1 Trial Design

This is a single-arm, single-center, open-label trial of pembrolizumab (MK-3475) in subjects with advanced gastric or gastroesophageal junction (GEJ) adenocarcinoma who have progressed after failure of any combination chemotherapy containing a platinum and a fluoropyrimidine agent.

Approximately 40 subjects will be enrollment to evaluate the efficacy and safety of pembrolizumab.

Enrollment will begin with all subjects without regard for PD-L1 expression status.

An evaluable specimen for PD-L1 status must be available and confirmed prior to enrollment.

All study subjects will be evaluated every 6 weeks (+/- 7 days) following the date of IP drug administration for the first six months and every 12 weeks (+/- 7 days) thereafter until progression of disease is documented with radiologic imaging (computed tomography or magnetic resonance imaging).

The primary efficacy endpoint is ORR (objective response rate) per mRECIST.

If a subject has progression of disease by mRECIST, it is recommended that the subject be discontinued from the study treatment unless, in the Investigator's opinion, the subject is deriving benefit from treatment.

Clinically stable subjects may continue to receive trial therapy at the discretion of the Investigator. If a repeat scan confirms progression of disease and the subject remains clinically stable, the subject may continue treatment .

Adverse events will be monitored throughout the trial and graded in severity according to the guidelines outlined in the NCI Common Terminology Criteria for Adverse Events (CTCAE) version 4.0.

[figure not shown]
Except as noted above, treatment with pembrolizumab will continue until documented disease progression, unacceptable adverse event(s), intercurrent illness that prevents further administration of treatment, Investigator's decision to withdraw the subject, subject withdraws consent, pregnancy of the subject, noncompliance with trial treatment or procedure requirements, completion of 24 months of pembrolizumab, or administrative reasons requiring the cessation of treatment.

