6.2 Primary genomic Objective(s) & Hypothesis(es)

(1) Objective: Integrative genomic analysis to identify predictive markers (i.e. immune signatures) and analyze the response rate according to molecular signatures identified through the ACRG effort.; Categorization: 1) mesenchymal, 2) MSI, 3) MSS-TP 53 intact, 4) MSS- TP53 mutation

Hypothesis: Association of response with tumor histology

Association of response with molecular signatures at baseline

Activation of immune pathways post treatment and association with response

Be good response to Pembrolizumab in MSS-MSI molecular and high-mutational burden type

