6.3 Exploratory Objective

- (1) **Objective:** Genomic analysis: Whole Exome Sequencing at baseline, RNA-seq pre and post (WES will be performed at SMC and analyzed together with the BI team at MERCK MSD (GpGx CSB and PGx Groups, Drs. [name], [name], [name], [name] and [name]) and SMC (Genome Center and Molecular Pathology).
- (2) As an exploratory analysis, we will isolate T cells using FACS sorting and sequence these cells. In addition, in order to identify the relationship between neoantigen drivers

like infection and response to pembrolizumab, we will prospectively collect serum antigens from blood at baseline.

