The preliminary data showed a Not significant correlation between PD-L-1 expression and ORR (P=0.071).

Given the mutual association of tumor genetic markers, gene expression and potential markers of response to immune therapy identified through the collaborative work between SMC and MERCK MSD and Lilly, we plan to perform a phase II study with integrative genomic analysis (whole exome and RNA sequencing) in pre and post biopsy specimens to better define those GCs who may benefit from pembro.

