- q. An optional newly-obtained core or excisional biopsy (FNA not adequate) is requested at any post-treatment time point during the study, (preference would be as close to dosing at Week 12 as possible). A biopsy is also requested at the time of discontinuation for PD, but will not be required. Endoscopic biopsies are permitted.

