11.1.1.2 Biomarker

To explore and identify biomarkers (inform the scientific understanding of diseases and/or their therapeutic treatment), the contingency tables will be presented by response for each of tumor histology, molecular signatures, immune pathways and etc..

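### Section 11.1.1.2 should add an exploratory within-patient change comparison for immune pathways and show progression-triggered tissue apart from on-treatment tissue (low severity, cheap to do)

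*Combined protocol and SAP*

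**What the plan says.** Section 6.2, under the primary genomic objective, lists the hypothesis "Activation of immune pathways post treatment and association with response". Section 6.3, headed exploratory, plans "RNA-seq pre and post", and the rationale in section 7.2.1 describes "integrative genomic analysis (whole exome and RNA sequencing) in pre and post biopsy specimens".

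The whole analysis text is in section 11.1.1.2: "the contingency tables will be presented by response for each of tumor histology, molecular signatures, immune pathways", followed by an open-ended list ending. That ending extends the list of factors, not the methods. The section names no test, no change measure, no rule for turning a pathway score into a table category, and no rule for choosing among several specimens.

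Tissue collection is set out in section 9.1. The flow chart row "Archival and/or Newly-Obtained Tissue Collection" has one entry for screening, one spanning the treatment cycles with footnote q, and one at End of Treatment. Footnote q says of the optional on-study core or excisional biopsy that it "is requested at any post-treatment time point during the study, (preference would be as close to dosing at Week 12 as possible". It then adds: "A biopsy is also requested at the time of discontinuation for PD, but will not be required".

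**The concern.** Two features of the plan fit poorly together.

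First, activation after treatment is naturally a change within a patient, measured here by sequencing before and after. A contingency table by response reduces that change to a category that the plan does not define. The continuous score, which carries more of the information when pairs are few, is not used.

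Second, the post-treatment tissue is of two kinds. Timing of the optional biopsy is loose but not tied to outcome by design. The biopsy at discontinuation for progression is triggered by an event closely related to response, the other axis of the table. If both kinds enter one table and immune activation differs between them, part of any link with response, or of its absence, would reflect when and why tissue was taken.

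What is at stake is the reading of one exploratory biomarker result. It is not trivial to the trial's purpose, since section 11.2 adds 17 of the 40 patients for biomarker work.

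**Working it through.** **Plan's own figure.** The documents give no figure for the paired-tissue analysis. The only sample-size figure is 23 for ORR (0.05 against 0.25, two-sided 0.05, power 0.80). The arcsine formula reproduces it: h = 2·asin(√0.25) − 2·asin(√0.05) = 0.596, and (1.960 + 0.842)² / 0.596² = 22.08, rounded up to 23. Adding 17 gives 40. This neither supports nor weakens the point.

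**Could mixing distort the table?** Biopsy uptake, the share taken at progression and activation rates are not in the documents, so everything here is assumed and illustrative. Let r and f be the shares of responder and non-responder specimens taken at progression, p the activated share in progression tissue, and 50% the activated share in on-treatment tissue. There is no true difference by response.

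a = (1 − r)·0.5 + r·p; b = (1 − f)·0.5 + f·p; OR = [a/(1 − a)] / [b/(1 − b)]

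| r | f | p | a | b | OR |
|---|---|---|---|---|---|
| 0.2 | 0.25 | 0.2 | 0.44 | 0.425 | 1.06 |
| 0.2 | 0.25 | 0.3 | 0.46 | 0.45 | 1.04 |
| 0.2 | 0.25 | 0.7 | 0.54 | 0.55 | 0.96 |
| 0.2 | 0.5 | 0.2 | 0.44 | 0.35 | 1.46 |
| 0.2 | 0.5 | 0.3 | 0.46 | 0.40 | 1.28 |
| 0.2 | 0.5 | 0.6 | 0.52 | 0.55 | 0.89 |
| 0.2 | 0.5 | 0.7 | 0.54 | 0.60 | 0.78 |
| 0.3 | 0.25 | 0.2 | 0.41 | 0.425 | 0.94 |
| any | any | 0.5 | 0.50 | 0.50 | 1.00 |

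The distortion can go either way and vanishes if activation does not depend on sampling condition.

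**Against the noise.** At the assumed 25% ORR, 40 patients give 10 responders and 30 non-responders. At an assumed 60% uptake, 6 and 18 have tissue. With a = 0.44 and b = 0.35, the standard error of the log odds ratio is √[1/(6·0.44) + 1/(6·0.56) + 1/(18·0.35) + 1/(18·0.65)] = 0.96. A 95% interval then spans a factor of exp(1.96·0.96), about 6.5, each way. The largest case, 1.46, lies ln(1.46)/0.96 = 0.4 standard errors from no effect.

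**What a paired comparison could deliver.** Start from the same 6 and 18 and set progression-discontinuation tissue aside:

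- Responders: 6 × 0.8 = 4.8, about 5.
- Non-responders: 18 × 0.5 = 9, or 18 × 0.75 = 13.5, about 14.
- Simulated mean half-width of the exact rank interval for the shift (normal scores): 1.29 SD of the change score at 5 vs 9 (95.8% level) and 1.17 SD at 5 vs 14 (95.6% level).

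At 30% uptake the counts are 3 × 0.8 = 2.4 (about 2) against 9 × 0.5 = 4.5 or 9 × 0.75 = 6.75 (about 4 to 7). The smallest two-sided rank p-value is 2 divided by the number of possible group assignments. For 2 vs 7 this is 2/36 = 0.056 and for 3 vs 4 it is 2/35 = 0.057, so no exact 95% interval exists. For 3 vs 5 it is 2/56 = 0.036, and one does.

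These counts are upper-side, because also setting aside on-treatment tissue taken after first progression would reduce them further.

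**The case against.** The case against is substantial and much of it stands.

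- **A reader might infer that the plan pools the two tissues.** It does not say so. The flow chart enters End-of-Treatment tissue separately, and footnote q describes the two biopsies in separate sentences, so they can be told apart. But that is a collection schedule. No analysis text uses the distinction.
- **A reader might infer that progression tissue means non-responder tissue.** The link is only partial. Responders who later progress can give it, and under section 5.1 "Clinically stable subjects may continue to receive trial therapy at the discretion of the Investigator" after progression.
- **A reader might infer an inflated false-positive rate.** Section 11.1.1.2 plans no test. Error rates for pooled tissue can be simulated, but only by supplying a test, an uptake and a progression share that the plan does not give.
- **A reader might infer that a table cannot capture change.** It can, if its category is built from the change between specimens. The fair criticism is that the category is undefined and the continuous change unused. The loss cannot be expressed as a percentage, because the plan sets no cut-point.
- **The remedy does not remove outcome-dependent sampling.** The first scan is at 6 weeks (footnote o) and Week 12 is the preferred biopsy time, so patients who progress and stop early are largely missing from an on-treatment comparison. This stands and must be stated with the result.

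Section 6.2 carries the label primary, but section 6.3 lists the sequencing as exploratory and section 11.2 describes the added patients as being for exploration. That supports a low severity. It does not make the change pointless, since a descriptive table can also mislead through its sampling.

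**Conclusion.** The point holds as a low-severity, cheap improvement. The stated hypothesis concerns post-treatment activation, the data will be paired and continuous, and the planned display uses no continuous within-patient change. Nothing in the analysis text keeps progression-triggered tissue apart from on-treatment tissue.

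The size of any distortion is unknown. Assumed inputs give odds ratios from 0.78 to 1.46, and even the largest is small beside sampling error at plausible counts. The documents do not support a claim that results will be biased in a given direction, or that the ORR result or sample size is affected. The case for change rests on a better-matched method at negligible cost, not on a demonstrated error.

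**What to change.** In section 11.1.1.2:

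1. Keep the contingency table. Beside it, compare within-patient change (post minus baseline) in the continuous pathway score between responders and non-responders, with a rank-based shift estimate and exact interval, labelled exploratory. Where pairs are too few for a 95% interval (for example 3 vs 4), show individual paired values only.
2. Base this comparison on biopsies taken after first dose, while on treatment and before first mRECIST progression, using the one nearest Week 12 if there are several. Show three other groups separately, without pooling: on-treatment tissue taken after first progression, tissue at discontinuation for progression, and tissue taken after stopping for other reasons. The last group needs a place because sections 8.6.1 and 10.1.4.1 allow stopping after complete response, and the End-of-Treatment tissue entry is not limited to progression. Add a sensitivity analysis that includes the on-treatment post-progression tissue.
3. Report biopsy counts, reason and days from first dose by response, and state that results are conditional on having on-treatment tissue.

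The cost is SAP wording and a recorded date and reason for each specimen. It needs no added biopsies, visits or patients, and footnote q can stay. The downside is fewer pairs, with early progressors under-represented in the main comparison. The separate displays keep visible those who gave tissue.

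As a separate matter that does not bear on this point, newly obtained baseline tissue is limited to 42 days before Day 1 in section 8.1.2 (criterion 7a) and to 12 weeks in section 10.1.2.5. The two should be reconciled.
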